2 INTRODUCTION

2.1 Study Rationale

[Part A]

AstraZeneca is developing AZD8233, a PCSK9 targeted antisense oligonucleotide (ASO) for the reduction of circulating levels of LDLs, a major cardiovascular disease (CVD) risk factor. Patients with dyslipidemia have increased risks of CVD events compared with the general population. Low levels of LDL-C are associated with a monotonically lower risk of incident atherosclerotic CVD events. The blood level of LDL-C is decreased by inhibiting PCSK9 from binding to LDL receptors (LDLRs) and by promoting the uptake of LDL-C into hepatocytes.

In the US, the Phase 1, MAD study, is being conducted to assess the safety and tolerability of AZD8233 and to characterize its PK following SC administration of multiple ascending doses. The study is also assessing the PD of AZD8233 by investigating its effect on levels of LDL-C and PCSK9 following SC administration of ascending doses.

According to the Japanese Guideline for General Considerations for Clinical Trials (ICH-E8, June 1995), patients who have mild hyperlipidaemia alone are permitted to be included in the phase I studies of investigational products for hyperlipidaemia.

Therefore, dyslipidaemic patients with a moderately increased LDL-C will be selected for the study.

The objective of Part A of the study is to investigate the safety and tolerability of AZD8233, following SC administration of multiple doses in a limited number of Japanese patients with dyslipidemia before progressing to part B of the study. Part A of the study will also investigate the PK and the PD of AZD8233.

CCI is the highest repeated administered dose that has been evaluated in a multiple dosing study conducted in the US (Study D7990C00002) and is also the highest planned dose to be evaluated in dose finding studies in Western populations. A dose of **CCI** per month is expected to result in close to the maximum achievable reduction in PCSK9 as well as LDL-C levels over the dose interval with AZD8233.

[Part B]

AZD8233 is a PCSK9-targeted ASO for the reduction of circulating levels of LDL-C. This study part aims to evaluate the dose-dependent reduction in LDL-C after SC administration of multiple doses of AZD8233 as well as the associated adverse effects profile. The data

generated will be used to guide choice of doses, dosing regimens, and sample sizes, as well as safety and PD monitoring in the further clinical development program.

[Part C]

The objective of Part C of the study is to investigate the safety and tolerability of AZD8233 [REDACTED] following SC administration of multiple doses (QM dosing) in a limited number of Japanese patients with dyslipidemia before progressing to Ph3. Part C of the study will also investigate the PK and the PD of AZD8233. This dose has been evaluated in the ongoing D7990C00004 study (SOLANO) , and is also the planned dose to be evaluated in Ph3.

2.2 Background

Dyslipidemia, particularly elevated levels of plasma LDL-C, is a main risk factor for CVD. Hypercholesterolemia is typically caused by a combination of environmental and genetic factors. Statin therapy is the standard lipid lowering medication for both secondary and primary preventions of CVD, as an adjunct to diet. Reduction of LDL-C by statins leads to a significant reduction in cardiovascular events ([Collins R et al 2016](#)). Statins reduce LDL-C by inhibiting 3 hydroxy 3 methyl glutaryl coenzyme A (HMG-CoA) reductase, the rate limiting enzyme of hepatic cholesterol synthesis. However, despite the substantial benefits of statin therapy, many patients do not reach LDL-C targets and some continue to be at residual risk despite maximum doses; for others, side effects such as myalgia and myositis may preclude statin use.

Genetic studies have identified PCSK9 as an important, HMG-CoA-independent circulating regulator of LDL-C ([Cohen J et al 2005](#), [Cohen J et al 2006](#)). Gain of function mutations in PCSK9 causes familiar dominant hypercholesterolemia; loss of function is associated with low circulating levels of LDL-C and a reduced risk of major vascular events. Circulating PCSK9 is derived mainly from the liver and increases LDL-C by promoting degradation of hepatic LDL receptors.

Two monoclonal antibodies (evolocumab [Amgen] and alirocumab [Sanofi/Regeneron]) have been successfully developed to pharmacologically inhibit circulating PCSK9. Injection of these compounds lowers LDL-C levels by approximately 60%, even in subjects already receiving maximum dose statin therapy ([Sabatine MS et al 2017](#), [Ray KK et al 2017](#)).

Based on the significant clinical benefit of PCSK9 inhibition, AstraZeneca is developing a PCSK9 targeted-N acetylgalactosamine-conjugated ASO specifically inhibiting intracellular PCSK9 expression in the liver ([Prakash TP et al 2014](#)). The potential risks identified for AZD8233 based on ASO class are presented in [Table 4](#). AZD8233 may provide novel treatment options to patients with dyslipidemia.

In the ongoing SAD (Study D7990C00001), global MAD (Study D7990C00002), this study

(Study D7990C00006), and global dose ranging (Study D7990C00003 [ETESIAN]) studies, > 120 participants have been exposed to multiple doses of subcutaneous administration of AZD8233.

The majority of the AEs reported have been mild or moderate. Injection site reactions (ISRs) have been reported in some participants, of which one was discontinued from treatment.

A total of six participants presented treatment-emergent ALT increases between $3 \times$ ULN and $< 6 \times$ ULN (max = 268 U/L). No increase in total bilirubin has been observed in any of these participants, and no clinical signs or symptoms have been associated. In all 6 participants, the elevation in ALT was transient, and all participants recovered while still in the study (3 on continued treatment, and 3 that had discontinued).

Except for these findings, there have been no indications of ASO-related platform risks, including thrombocytopenia (platelet counts have remained stable in all participants), renal injury, impaired blood coagulation, complement activation, hypersensitivity/anaphylactic reaction, and flu-like reactions. Results on ADA from ongoing studies are not yet available. Overall, AZD8233 has been generally well tolerated at all doses studied with no significant safety findings on vital signs, ECG, body temperature, haematological, or clinical chemistry safety lab parameters.

Preliminary data from Study D7990C00001 showed that AZD8233 doses of \geq CCI reduced PCSK9 by $\geq 90\%$ and LDL-C by as much as 70%.

A detailed description of the chemistry, pharmacology, efficacy, and safety of AZD8233 is provided in the Investigator's Brochure ([Investigator's Brochure 2021](#)).

2.3 Benefit/Risk Assessment

Potential risks of AZD8233 and mitigation strategy are shown in [Table 4](#). More detailed information about the known and expected benefits and potential risks of AZD8233 may be found in the Investigator's Brochure.

2.3.1 Risk Assessment

Table 4 Risk Assessment

Potential risk of clinical significance	Rationale for risk	Mitigation Strategy
Study intervention		
Thrombocytopenia	
Severe thrombocytopenia has been observed in some ASO programs and it is not known whether other members of the class may be affected (Crooke ST et al 2017). One case of severe thrombocytopenia was observed in a non-human primate toxicology study with AZD8233.
	
Monitoring of platelet count. In case of severe thrombocytopenia, the action plan detailed in Appendix F will be followed.

Kidney injury	
The kidney is an oligonucleotide high-uptake tissue. Tubular necrosis has been observed with ASOs including an ASO inhibiting PCSK9. This was not observed in toxicology studies with AZD8233 (Van Poelgeest EP et al 2013, Van Poelgeest EP et al 2015, Van Meer L et al 2017).
	
Monitoring of S-creatinine, BUN, urine albumin, and urine total protein as well as calculation of eGFR.

Liver Toxicity - Transaminase Elevation	
The liver is an oligonucleotide high-uptake tissue (Hung G et al 2013). Oligonucleotide treatment may cause transient transaminase elevations in mice, monkeys, and humans at therapeutic exposures (Burdick AD et al 2014, Hagedorn PH et al 2013, Hildebrandt Eriksen ES et al 2012). AZD8233 is a GalNAc conjugated oligonucleotide, utilizing the ASGP-R to enhance the uptake by hepatocytes. In the 6-month mouse chronic toxicology study, higher levels in liver enzymes (AST and ALT) in males and/or in females was observed and minimal to mild histopathological changes in few animals at high doses, however deemed not to be adverse.
	
Monitoring a panel of liver safety biomarkers including transaminases

Potential risk of clinical significance	Rationale for risk	Mitigation Strategy
	In ongoing clinical studies with AZD8233, transient increases in transaminases have been seen in 6 participants (see Section 2.2 for details).	
Antidrug Antibodies	There is a potential risk for antibody formation. Emergence of ADA has been observed in a proportion of clinical study participants after repeated oligonucleotide treatment, leading to change in the PK profile. To date, no apparent association of ADA with loss of efficacy or safety findings has been observed.	Assessment of ADAs and monitoring for immunogenicity effects (including hypersensitivity reactions and ADA effect on PK/PD). Guidance on the definition of an anaphylactic reaction and the action plan that needs to be followed with regards to ADA sampling are presented in Appendix G .
Injection Site Reactions	
As with any exogenous substance, injection site reactions may occur as a response to the SC injection of AZD8233. Possible risks associated with SC administration are redness, swelling, pain, induration, and sometimes infection at the administration site. There have been reports in some ASO programs of a few cases of severe ISRs with a high incidence of discomfort to the patient that have led to withdrawal from treatment.
 
In the ongoing clinical programme for AZD8233, mild ISRs have been observed in a few participants (see Section 2.2 for details).
	Monitoring for injection site reactions
Complement Activation	
This is a known class effect of oligonucleotides and appears to be directly plasma concentration (C_{max}) driven. Monkeys are considered more sensitive to complement activation than humans (Crooke ST et al 2016).
 
In the 9-month monkey study, minimal to mild higher complement Bb was observed at ≥ 6 mg/kg/occasion at the end of the
	Assessment of complement activation around C_{max} ($C3a$ [Part A only], $C5a$, Bb)

Potential risk of clinical significance	Rationale for risk	Mitigation Strategy
	study and correlated microscopically with mononuclear cell (predominantly lymphocytic) infiltration/inflammation observed in multiple tissues, including the administration site.	
Inhibition of Intrinsic Coagulation Pathway	
Increases in aPTT, in the absence of clinical or pathological sequelae, have been observed with ASOs (Burel S et al 2013, Henry SP et al 1997). Mechanistically, interaction of ASOs with the intrinsic tenase complex and thrombin results in a selective inhibition of the intrinsic clotting cascade and hence aPTT was prolonged. (Henry SP et al 2017, Sheehan JP, Lan HC 1998, Sheehan JP, Thao PM 2001).
 
Changes in activity of the intrinsic clotting pathway reverse when ASOs are cleared from plasma. Transient prolongation of aPTT has been described in man and was observed to correlate in a linear manner with the C_{max} at the end of infusion (Sewell KL et al 2002).
 
There were no treatment related changes in any coagulation parameters in the nonclinical toxicology studies
	Assessment of aPTT and PT
Hypersensitivity and Anaphylactic Reaction	Similar to any foreign biological agent, administration of AZD8233 may induce hypersensitivity reactions. These acute reactions are important because they may be severe but are considered rare.	Monitoring for immunogenicity effects (severe allergy and hypersensitivity reactions and ADA), see Appendix G
Flu-like Reactions	Flu-like symptoms (chills, myalgia, arthralgia, feeling hot, and body temperature increase) are rather common for some ASOs. No indications of systemic inflammatory effects induced by	Monitoring for any flu-like symptoms and assessment of hs-CRP

Potential risk of clinical significance	Rationale for risk	Mitigation Strategy
	AZD8233 have been seen in the toxicology studies.	
Study procedures		
Subcutaneous Injection	Pain near the injection site (for 1 or 2 days) is the most common complication of subcutaneous injections.	Slow injection of AZD8233 using gentle pressure (at least 5 seconds duration is recommended) and rotation of injection sites.

ADA = antidrug antibody; aPTT = activated partial thromboplastin time; ASGP-R = asialoglycoprotein receptor; ASO = antisense oligonucleotide; BUN = blood urea nitrogen; C_{\max} = maximum plasma concentration; eGFR = estimated glomerular filtration rate; hsCRP high sensitive C reactive protein; IB = Investigator's Brochure; ISR = injection site reaction; PCSK9 = proprotein convertase subtilisin/kexin type-9; PT = prothrombin time; PD = pharmacodynamics; PK = pharmacokinetics; SC = subcutaneous

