12-lead ECG ^c	X		X	X		X		X		X	X ^j	X	Section 8.2.3
Serum chemistry	X		X	X	X	X	X	X	X	X	X	X	Section 8.2.4
Hematology	X		X	X	X	X	X	X	X	X	X	X	Section 8.2.4
Coagulation parameters	X		X	X	X	X	X	X	X	X	X	X	Section 8.2.4
hs-CRP	X		X					X		X	X	X	Section 8.2.4
Complement activation panel ^d			X			X		X					Section 8.2.4
Urinalysis	X		X	X	X	X	X	X	X	X	X	X	Section 8.2.4
Urine renal safety biomarkers	X		X	X	X	X	X	X	X	X	X	X	Section 8.2.4
Pharmacodynamics													
LDL-C ^e		X	X	X	X	X	X	X	X	X	X	X	Section 8.5.3.1
PCSK9 ^e		X	X	X	X	X	X	X	X	X	X	X	Section 8.5.3.1

Table 2 Schedule of Activities (Part B)

	Screening		Treatment Period							EDV	Follow-up period ⁿ	Final Follow-up Visit ⁿ	Corre-sponding Section in Protocol
Visit Number	1	2	3	4	5	6	7	8	9		10, 11, 12, 13, 14, 15	16	
Study Week			0	1	3	4	6	8	10		12, 14, 16, 18, 20, 22	24	
Study Day	Days -28 to -10	Days -7 to -4	Day 1	Day 8	Day 22	Day 29	Day 43	Day 57	Day 71		Days 85, 99, 113, 127, 141, 155	Day 169	
Visit Window				± 1 day	± 2 days		± 2 days	± 2 days					
Triglycerides ^e		X	X	X	X	X	X	X	X	X	X	X	Section 8.5.3.1
Other lipid parameters ^e			X	X	X	X	X	X	X	X	X	X	Section 8.5.3.1
Pharmacokinetics													
Plasma sample for total full length ASOs of AZD8233 ^f				X		X	X	X	X	X	X ^f	X	Section 8.5.1
Immunogenicity													
Samples for anti-AZD8233 antibodies ^g			X	X		X		X		X	X ^g	X	Section 8.5.2
Exploratory biomarker analysis													
Biomarker analyses (plasma) ^e	X		X	X	X	X	X	X	X	X	X	X	Section 8.6.1
Biomarker analyses (urine) ^e			X	X	X	X	X	X	X	X	X	X	Section 8.6.1
Genomics Initiative optional, exploratory genetic sample ^h			X										Section 8.7

ADA = antidrug antibody; BMI = body mass index; D = day; ECG = electrocardiogram; EDV = early discontinuation visit; FSH = follicle-stimulating hormone; HbA1c = haemoglobin A1c; hs-CRP = high sensitive C-reactive protein; LDL-C = low-density lipoprotein cholesterol; LH = luteinizing hormone; PCSK9 = proprotein convertase subtilisin/kexin type-9; PK = pharmacokinetic; IMP = Investigational medicinal product

Subjects are required to be fasted for at least 10 hours overnight prior to all study visits except for Visit 1; subjects are permitted to drink water during this period of fasting until 1 hour before blood sampling. On days when subjects attend the clinic in a fasting state, blood and urine samples should be obtained prior to administration of the IMP.

Samples to be obtained from all treatment arms unless specified in the table.

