- a Weight should be measured in light indoor clothes, without shoes, after using the bathroom. Otherwise, follow the local standard procedure.
- b Injection Site Reaction assessments to be collected based on adverse event collection criteria.
- c Vital signs and ECG to be measured pre-dose on dosing days.
- d Blood samples for complement activation panel will be taken around C_{max} and are to be collected pre-dose and 2 hours (± 5 minutes) post-dose.
- e Samples to be obtained pre-dose on dosing days.
- f PK sampling to be performed at Visits 4 (Day 8), 6 (Day 29), 7 (Day 43), 8 (Day 57), 9 (Day 71), 10 (Day 85), 12 (Day 113), 14 (Day 141), and final follow-up visit/EDV. Schedule of sampling for Visit 6 (Day 29), 8 (Day 57) is shown below.
Visit 6 (Day 29): pre-dose, Visit 8 (Day 57): pre-dose.
- g ADA sampling to be performed at Visits 3 (D 1), 4 (D 8), 6 (D 29), 8 (D 57), 10 (D 85), 12 (D 113), 14 (D 141), and final follow-up visit/EDV. ADA samples to be collected pre-dose on all dosing days.
- h If, for any reason, the sample is not drawn pre-dose on Visit 3 (Day 1), it may be taken at any visit until the final follow-up/EDV visit.
- i Check screening labs and inclusion/exclusion criteria.
- j ECG to be performed during the follow-up period at Visits 10 (Day 85), 11 (Day 99), 13 (Day 127), and 15 (Day 155).
- k Pregnancy test: Serum β -human chorionic gonadotropin (β -hCG) will be performed on all the women participants, irrespective of childbearing potential.
- l Pregnancy test (Day 1): Urine pregnancy test using dipstick will be performed before randomization on all the women participants, irrespective of childbearing potential, at a local laboratory.
- m All the women participants should have FSH and LH levels determined, irrespective of childbearing potential.
- n In the case of early discontinuation, follow-up visit will be performed every 2 weeks after last dose.

[Part C]

Randomization should only proceed if all required assessments have been performed and all inclusion/exclusion criteria as well as other protocol restrictions have been evaluated; see Sections [5](#) and [6.5](#).

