Study Day/Week	Days -28 to -4	Day -1	Days 1 to 3	Day 8 ^a	Day 29	Days 15, 22, 36, 44	Day 56	Days 57 to 59	Weeks 2, 4, 6, 8, 10, 12, 14 (after last dose)	Week 16 (after last dose)	
Visit Window	-	-	-	-	± 1 day	± 1 day	± 1 day		± 2 days	± 2 days	
Cardiac telemetry		X (for at least 4 h)	X (pre-dose to 24 h post-dose)					X (pre-dose to 24 h post-dose)		Section 8.2.3	
Hematology, Chemistry and Coagulation including hs-CRP)	X	X	X (24 h post-dose)	X	X (pre-dose)			X (pre-dose) (Week 2, 4, 8 and 12 after last dose)	X	Section 8.2.4	
Sampling for renal safety biomarkers	X		X (pre-dose and then 24 and 48 h post-dose)	X	X (pre-dose)			X (pre-dose)		Section 8.2.4	

	Screening	Treatment Period							Follow-up Period		Corre-sponding Section in Protocol
		1	2	3	6	4, 5, 7, 8	9	10 to 16	17 (Final Follow-up Visit/ ED Visit)		
Visit Number	1	2	3	6	4, 5, 7, 8	9	10 to 16	17 (Final Follow-up Visit/ ED Visit)	Week 16 (after last dose)	Corre-sponding Section in Protocol	
Study Day/Week	Days -28 to -4	Day -1	Days 1 to 3	Day 8 ^a	Day 29	Days 15, 22, 36, 44	Day 56	Days 57 to 59	Weeks 2, 4, 6, 8, 10, 12, 14 (after last dose)	Week 16 (after last dose)	
Visit Window	-	-	-	-	± 1 day	± 1 day	± 1 day		± 2 days	± 2 days	
Sampling for dipstick urinalysis for hematuria	X		X (pre-dose and then 24 and 48 h post-dose)	X	X (pre-dose)			X (pre-dose)			Section 8.2.4
Sampling for platelet count	X	X	X (24 and 48 h post-dose)	X	X (pre-dose)	X (Days 22, 44)	X		X		Section 8.2.4
Complement activation panel ^h			X (pre-dose and then 1, 2 and 4 h post-dose)					X (pre-dose and then 1, 2 and 4 h post-dose)			Section 8.2.4
Immunogenicity											
Samples for anti-AZD8233 antibodies			X (pre-dose)		X (pre-dose)			X (pre-dose)	X (Week 2 after last dose)	X	Section 8.5.2

	Screening	Treatment Period							Follow-up Period		Corre-sponding Section in Protocol
		1	2	3	6	4, 5, 7, 8	9	10 to 16	17 (Final Follow-up Visit/ ED Visit)		
Visit Number	1	2	3	6	4, 5, 7, 8	9	10 to 16	17 (Final Follow-up Visit/ ED Visit)	Week 16 (after last dose)	Corre-sponding Section in Protocol	
Study Day/Week	Days -28 to -4	Day -1	Days 1 to 3	Day 8 ^a	Day 29	Days 15, 22, 36, 44	Day 56	Days 57 to 59	Weeks 2, 4, 6, 8, 10, 12, 14 (after last dose)	Week 16 (after last dose)	
Visit Window	-	-	-	-	± 1 day	± 1 day	± 1 day	± 1 day	± 2 days	± 2 days	
Pharmacodynamics											

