4.3 Justification for Dose

[Part A]

In the Phase 1 SAD study (Study D7990C00001), which has been conducted in the US, single SC doses of AZD8233 up to **CCI** have been well tolerated in participants with elevated LDL-C.

The dose to be evaluated in Part A is **CCI**.

This is the highest dose that has been evaluated in the MAD study (Study D7990C00002) conducted in the US, and is also the highest planned dose to be evaluated in Part B. A dose of **CCI** monthly is expected to result in close to the maximum achievable reduction in PCSK9 and hence LDL-C levels over the dose interval with AZD8233.

One extra dose (loading dose) is planned to be administered one week after the first dose with the purpose to reach steady state conditions more quickly in trough concentrations (assumed to reflect tissue concentrations). As the loading dose is administered after the initial large decline in plasma concentrations of the first dose, the loading dose is predicted to result in minimally higher C_{max} or AUC_{0-48} as compared to the first single dose. Thus, a total of 4 doses are planned to be administered to each subject, i.e., dosing on Days 1, 8, 29, and 57.

A dose of **CCI** monthly is expected to result in a mean C_{max} and AUC_{0-48} at steady state at approximately half the exposure limits defined from the NOAEL dose in a 3-month toxicity study in cynomolgus monkeys. From a safety perspective, risks observed in other ASO development programs can be divided into acute and chronic risks. Acute risks, as those related to C_{max} , including transient increase in activated partial thromboplastin time (aPTT), are expected to occur very soon after dosing. Chronic risks, like reduction of platelet count and development of ADAs have, if at all, most often appeared after more than 3 months of dosing.

Taken together, the benign safety profile observed for single doses of AZD8233 up to **CCI**

support initiation of Part B after the SRC will review safety data up to 7 days after last dose administration in Part A. Data later than Day 64 (if available) may be reviewed by the SRC as needed.

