Visit 3 (randomization): Visit 3 (Day 1) should be performed within 28 days of Visit 1. Participants are required to fast for at least 10 hours overnight prior to the visit; participants are permitted to drink water during this period of fasting until 1 hour before blood sampling. At Visit 3, the eligibility criteria must be verified by checking screening labs and inclusion/exclusion criteria. A complete physical examination must be performed. Blood and urine samples are to be obtained prior to administration of study intervention in fasted state. An ADA sample will be obtained pre-dose. Vital signs and ECG are to be checked. If the participant fulfills all inclusion criteria and none of the exclusion criteria, he/she will be randomized in IXRS, and the study intervention will be administered as an SC injection.

Treatment visits (Visits 4- 9): Visit 4 (Day 8 ± 1 day), Visit 5 (Day 22 ± 2 days), Visit 6 (Day 29 ± 2 days), Visit 7 (Day 43 ± 2 days), Visit 8 (Day 57 ± 2 days) and Visit 9 (Day 71 ± 2 days) are planned as clinical visits. At Visits 6 and 8, the study intervention will be administered as an SC injection. Participants are required to fast for at least 10 hours prior to Visits 4, 6, and 8. They are permitted to drink water during this period of fasting until 1 hour before blood sampling. Blood and urine sampling must be performed prior to administration of study intervention. PK sampling to be performed at Visits 4, 6, 7, 8, and 9. At Visits 4, 6, and 8, PK and ADA sampling must be done pre-dose when the study intervention will be administered. An abbreviated physical examination is required at the visits. Vital signs and blood and urine samples are to be taken at the visits. ECG must be performed at Visits 4, 6 and 8.

Follow-up visits (Visits 10-15): ECG must be performed at Visit 10 (Day 85 ± 2 days), Visit 11 (Day 99 ± 2 days), Visit 13 (Day 127 ± 2 days), and Visit 15 (Day 155 ± 2 days). At all follow-up visits, an abbreviated physical examination is required, and vital signs, blood, and urine samples are to be checked. PK and ADA sampling is to be performed at Visit 10, Visit 12 (Day 113 ± 2 days), and Visit 14 (Day 141 ± 2 days).

Early Discontinuation Visit: The EDV may take place any time during the study, in case a participant discontinues study treatment prior to Visit 8 (where the last dose of study treatment is administered). The same assessments as during the final follow-up visit will be performed. See Section 7.1.

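### No scheduled coagulation sample falls within 12 h of a dose, so the plan would probably miss the brief, peak-related aPTT prolongation that the protocol describes

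*Protocol*

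**What the plan says.** **The risk.** Protocol Section 2.3.1, Table 4, lists inhibition of the intrinsic coagulation pathway as a potential risk of the oligonucleotide class. On timing it says "Transient prolongation of aPTT has been described in man and was observed to correlate in a linear manner with the" Cmax at the end of an infusion, and "Changes in activity of the intrinsic clotting pathway reverse when ASOs are cleared from plasma". Section 4.3 treats this as an acute, Cmax-related risk for this trial: such risks, "including transient increase in activated partial thromboplastin time (aPTT), are expected to occur very soon after dosing". The mitigation in Table 4 is "Assessment of aPTT and PT", with no timing.

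**The coagulation schedule (Section 1.3).**
- Parts A and C: the row "Hematology, Chemistry and Coagulation including hs-CRP" has samples at screening, Day -1, 24 h after the first dose, Day 8 (pre-dose in Part A, no dose in Part C), pre-dose on Days 29 and 57, and follow-up Weeks 2, 4, 8, 12 and 16.
- Part B: the row "Coagulation parameters" is marked at Visit 1 and at every visit from Visit 3, with no post-dose time. Section 8 adds, for the treatment visits: "Blood and urine sampling must be performed prior to administration of study intervention".

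**The comparator.** Table 4 also calls complement activation Cmax-driven, and there it asks for sampling at about the time of Cmax. In Parts A and C the complement panel is drawn pre-dose and at 1, 2 and 4 h on Days 1 and 57. In Part B the samples "are to be collected pre-dose and 2 hours" post-dose on Days 1, 29 and 57.

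The schedules in the three SAPs repeat the coagulation timing and add no early post-dose sample.

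**The concern.** The protocol gives two risks the same driver, peak plasma concentration. It times the measurements to the peak for one and not for the other, and does not explain the difference. If aPTT lengthens for a few hours after injection and then recovers, a trial run exactly to schedule could produce normal aPTT tables at every visit. Those tables would feed the safety objective in all three parts. Part C matters most, because it is the Japanese safety check of the regimen intended for Phase 3. The risk is that unremarkable summaries are read as showing no acute effect on coagulation, when the samples were taken too late to bear on that question.

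**Working it through.** The documents state no sample size, power or detection target for coagulation, so there is no figure of the plan's own to reproduce. The check is one of timing.

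**Step 1. Interval from each dose to the next scheduled coagulation sample** (Protocol Tables 1 to 3):

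| Part | Dose | Next coagulation sample | Interval |
|---|---|---|---|
| A | Day 1 | 24 h post-dose | 24 h |
| A | Day 8 | Day 29, pre-dose | 29 − 8 = 21 d |
| A | Day 29 | Day 57, pre-dose | 57 − 29 = 28 d |
| A | Day 57 | Follow-up Week 2 | 14 d |
| B | Day 1 | Day 8 | 8 − 1 = 7 d |
| B | Day 29 | Day 43 | 43 − 29 = 14 d |
| B | Day 57 | Day 71 | 71 − 57 = 14 d |
| C | Day 1 | 24 h post-dose | 24 h |
| C | Day 29 | Day 57, pre-dose | 57 − 29 = 28 d |
| C | Day 57 | Follow-up Week 2 | 14 d |

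In Parts A and C, Day 8 gives a second sample exactly 7 days after the first dose. Scheduled coagulation samples within 4 h of a dose: 0 in each part. Within 12 h: 0 in each part.

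**Step 2. How much of a peak effect might remain at the first sample?** Section 4.3 mentions a large initial fall in plasma concentration before the Day 8 dose but gives no rate. Assume, for illustration only, a peak at 2 h, an effect proportional to concentration, and a single early half-life h. The share of the peak effect left at 24 h is then 0.5^((24 − 2)/h):

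| Assumed h | Share left at 24 h |
|---|---|
| 2 h | 0.05% |
| 4 h | 2.2% |
| 6 h | 7.9% |
| 8 h | 14.9% |
| 12 h | 28.1% |

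Moving the assumed peak to 1 h or 4 h changes the ends of this range to 0.03%–26.5% and 0.10%–31.5%. At 168 h (7 days) the share is below 0.01% in every case. The terminal phase (half-life 2 to 3 weeks, Section 4.2) would add a low residual.

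**Step 3. What peak samples would add.** Suppose every affected participant shows the change at a peak draw. The chance of seeing at least one case is 1 − (1 − p)^n. With 8 active participants (Part A or C) and an assumed p of 10%, 20% or 30%, it is 57%, 83% or 94%. With about 40 active participants in Part B (two of three equal arms of 60), it is 98.5% at p = 10%.

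**The case against.** The case for leaving the schedule alone has substance.

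- **No signal for this compound.** Table 4 reports no treatment-related coagulation changes in toxicology studies and notes that class aPTT increases came without sequelae. Section 2.2 reports no indication of impaired coagulation in ongoing studies with more than 120 participants on repeated doses. This lowers the likelihood and seriousness of the risk. The documents do not say whether those studies sampled aPTT near the peak.
- **Complement is not a perfect comparator.** It had a compound-specific finding (higher Bb in the 9-month monkey study), and only its row in Table 4 asks for sampling near Cmax. A reader might infer that the coagulation schedule breaks a stated commitment. It does not, because no timing was promised. The mismatch is between the described mechanism and the sampling times.
- **The 24 h sample is not empty.** A reader might infer that the trial cannot detect any aPTT effect. The documents do not support that: an effect lasting to 24 h after the first dose could appear in Parts A and C, Section 8.2.4 allows unscheduled safety samples, and bleeding would be reported as an adverse event.
- **The human Cmax correlation comes from infusion**, whereas AZD8233 is given subcutaneously. Section 4.3 nevertheless applies the early, Cmax-related timing here.
- **PT.** The protocol ties only aPTT and the intrinsic pathway to the peak. Nothing supports extending the point to PT.
- **Other safeguards.** Bleeding-risk exclusions, the inpatient stay after the first and last doses in Parts A and C, and bleeding-event tables in Parts B and C limit clinical consequences. They do not measure aPTT at the peak.

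These points bear on likelihood and severity. None makes a sample at 24 h or later informative about a change lasting a few hours.

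**Conclusion.** The point holds for aPTT and for scheduled sampling. No scheduled coagulation sample in any part falls within 12 h of a dose; the shortest interval is 24 h in Parts A and C and 7 days in Part B. On the protocol's own account of the effect, the schedule would probably miss a brief peak-related change. That conclusion needs only the schedule and the protocol's description of the risk. The 0.05% to 28% range at 24 h also rests on assumed half-lives and an assumed linear effect, and is illustrative.

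A reader might infer that the sponsor will report no effect on coagulation. The SAPs plan only descriptive summaries and commit to no such statement. The supportable conclusion is narrower: normal aPTT summaries from this schedule are not evidence against a transient peak effect. Likelihood and severity are low on the reported evidence, but the remedy is cheap enough to be worth making.

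**What to change.** Reconcile Table 4, Section 4.3 and the schedules of activities, by amendment where dosing is still to come:

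- **Part C (Table 3):** add an aPTT tube to the complement draws at 1, 2 and 4 h on Days 1 and 57, and at Day 1 pre-dose. The Day 57 pre-dose coagulation sample already exists, so this is at most 3 + 3 + 1 = 7 new tubes per participant.
- **Part B (Table 2):** add an aPTT tube to the 2 h complement draw on Days 1, 29 and 57, which is 3 new tubes.
- **SAPs:** tabulate aPTT by nominal time. The Section 3.3.2 rule keeps one value per analysis visit window, so a by-visit table alone would not show the pre-dose and post-dose values side by side.
- **Participants already dosed:** state in the CSR that the coagulation data cannot exclude a transient Cmax-related aPTT effect. For Part A this is the only remedy left, since its SAP records changes made after database lock.

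The cost is a few mL of blood per participant, to be checked against the limits in Section 8 (800 mL in Parts A and C, 650 mL in Part B), and the assays. No new visit or venepuncture is needed.
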